## 3.4 Study Procedures

#### **3.4.1** Screening/Baseline Procedures

Subjects will be identified by study investigators within the academic urology practice at Cedars-Sinai Medical Center during routine clinical practice. All study assessments for eligibility are performed as part of standard of care. Once a patient has been diagnosed, expressed interest in HIFU, and recommended study participation, they will be presented with the Informed Consent Form, including a description of the study purpose, risks, benefits and possible alternatives. The prospective participant will be given sufficient time to consider participation in the research. Patients will be asked to sign the study consent form after receiving a complete explanation of the study.

This study will enroll patients with clinically localized, Gleason score 7-10 prostate cancer

localized to one lobe on prior biopsies or overall Gleason score 6 with  $\geq$  half of systematic biopsy cores positive and  $\geq$  50% of core involvement in at least one core, interested in HIFU as primary treatment. Patients with low Gleason grade cancer (e.g. Gleason grade 3) on the contralateral lobe are allowed since the standard-of-care for such low grade disease is observation. Patients with very low risk disease and low-volume, low-risk disease are excluded since their preferred management is active surveillance. Patients will present with newly diagnosed disease or after a period of active surveillance. If there is suggestion of extracapsular disease or seminal vesicle involvement on MRI, these patients will be excluded. Metastatic workup with cross sectional imaging and/or bone scan will not be mandatory, since they are not indicated for low- and intermediate-risk prostate cancers according to AUA and NCCN guidelines.

The pilot study will allow enrollment of patients scheduled to undergo radical prostatectomy performed either at Cedars-Sinai Medical Center (CSMC) or an outside hospital (OSH). If the radical prostatectomy is performed at an OSH, authorization from subjects will first be obtained. Then the final pathology report of the radical prostatectomy from OSH will be obtained, reviewed and considered at CSMC for final data analysis. Additionally, the outside pathology slides may need to be reviewed here at CSMC for final data analysis as well, however this decision will be made later. They will get a preoperative PET-hrMRI. All surgical interventions and postoperative care are per standard-of-care. Scan results may identify patients who do not qualify for surgery.

The investigator may decide to change arms for a subject (i.e. HIFU to RP or RP to HIFU) based on MRI finding or replace the subject after imaging review.

# Screening procedures include:

#### 3.4.1.1 Informed Consent

Informed consent must be obtained prior to any protocol assessment or procedure which is not performed as part of local routine care. Subjects must also grant permission to use protected health information per the Health Insurance Portability and Accountability Act (HIPAA). Signed and dated ICF and HIPAA for enrolled participants who are not subsequently screened or undergo study intervention will be maintained at the study site.

## **3.4.1.2** Medical history

Medical history (comorbidities) includes clinically significant diseases that are currently active or that were active, including past surgical history, medications, social history, family history including history of prostate cancer, dates of previous prostate biopsies, prostate biopsy pathology results, PSA results, dates and results of previous prostate imaging

## 3.4.1.3 Reporting on Concomitant medication

Any current concomitant medications and treatments will be recorded

# **3.4.1.4** Demographics

Age, ethnicity/race

# 3.4.1.5 Review subject eligibility criteria

All necessary procedures and evaluations must be performed to document that the subject meets all of the inclusion and none of the exclusion criteria.

# **3.4.1.6** Physical exam including vital signs, height, and weight

Physician directed physical exam. This may be collected within 180 days of screening. Vital Signs will include heart rate (pulse), respiratory rate, blood pressure, and body temperature.

#### **3.4.1.7** Adverse event assessment

Adverse events will be assessed at imaging, post imaging (biopsy), HIFU/Prostatectomy, and HIFU follow up. See section 5.1 and 5.2 for Adverse Event and reporting. Only grade 3 and above imaging-related AEs will be captured and all SAEs following the receipt of 18F-DCFPyL agent.

# **3.4.2** Study Calendar for Focal High-Intensity Focused Ultrasound (HIFU) Therapy

Procedure	Screening	lmaging	Post- imaging²	Standard of Care (SOC) Treatment	Post SOC Treatment 6 months (+/- 1.5 months) following HIFU
Informed Consent/Registration	X				
Review Eligibility	X				
Demographics	X				
Medical History	X				
Prior and Current Medication Review	Х				
Vital Signs 		X	X		
Physical Exam (including symptoms assessment, height, weight) 	Х				
Standard MRI with Gadolinium		X (at least one day prior to targeted prostate biopsy)			X (at least one day prior to targeted prostate biopsy)
Optional: Tissue collection 			Х		Х
Optional: Blood collection 	X 	X 7	X 	X 	X8

18-PSMA PET-hrMRI	X (at least one day prior to targeted prostate biopsy)			
Adverse Event Review	X	X	X	X
Hemigland or Focal High Intensity Focused Ultrasound (HIFU) 			X (performed within 4 months after mapping and/or targeted prostate biopsy)	
Standard Sextant Mapping Biopsy		X		Х
MR/US-fusion targeted biopsy		X 3		Х

- 1. Focal HIFU performed on study for patients with confirmed unilateral high grade prostate cancer.
- 2. End of study for bilateral Gleason ≥7 disease
- 3. Of any lesions with PI-RADS scores >3 on hr MRI or 18F-PSMA PET positivity
- 4. Tissue collection includes left over tissue from standard of care collection only.
- 5. Need to be obtained within 180 days of screening. Vital signs will be assessed before and after administration of 18F-DCFPyL.
- 6. Blood collection will be approximately 17 mL (approximately 1 tablespoon) of whole blood. As of August 2023, optional blood draw has been removed from ICF (MODCR00000250).
- 7. Pre-treatment blood will be drawn once before HIFU or on the day of surgery with standard of care blood draw.
- 8. Post-treatment blood will be drawn once after HIFU with standard of care blood draw.

Study Calendar for Radical Prostatectomy

Procedure	Screening	lmaging	Standard of Care (SOC) Treatment	Post SOC Treatment 6 months (+/- 1.5 months) following Prostatectomy
Informed Consent/Registration	Х			
Review Eligibility	X			
Demographics	X			
Medical History	X			
Prior and Current Medication Review	Х			
Vital Signs 		X		
Physical Exam (including symptoms assessment, height, weight) 	Х			

Standard MRI with Gadolinium		X (preoperative PET-hrMRI prior to prostatectomy)		
Optional: Tissue collection 			Χ	
Optional: Blood collection 	X 	X 4	X 	
18-PSMA PET- hrMRI		X (at least one day prior to prostatectomy)		
PSA Lab Result				X
Adverse Event Review		X	Х	Х
Prostatectomy			Х	

- 1. Tissue collection includes left over tissue from standard of care collection only.
- 2. Need to be obtained within 180 days of screening. Vital signs will be assessed before and after administration of 18F-DCFPyL.
- 3. Blood collection will be approximately 17 mL (approximately 1 tablespoon) of whole blood. As of August 2023, optional blood draw has been removed from ICF (MODCR00000250).
- 4. Pre-treatment blood will be drawn once before prostatectomy or on the day of surgery with standard of care blood draw.
- 5. Post-treatment blood will be drawn once after prostatectomy with standard of care blood draw.

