## Eligibility for HIFU

If subjects are found to have unilateral high grade disease (i.e. Gleason grade 4 or 5), they will be considered as a candidate for hemigland or focal HIFU therapy. Clinician judgment may be exercised in determining eligibility for HIFU, since established criteria based on volume and extent of disease do not exist. If patients have high grade disease in both lobes, they will not be eligible for HIFU therapy on this trial. Their data will be used to assess the primary endpoint but they will not be considered for secondary endpoints.

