#### Attribution categories are as follows:

- Definite The AE is clearly related to the study treatment.
- Probable The AE is likely related to the study treatment.
- Possible The AE may be related to the study treatment.
- Unlikely The AE is doubtfully related to the study treatment.
- Unrelated The AE is clearly NOT related to the study treatment.

Note: This includes all events that occur within 30 days of the last dose of protocol treatment. Any event that occurs more than 30 days after the last dose of treatment and is attributed (possibly, probably, or definitely) to the agent(s) must also be reported accordingly.

Step 4: Determine the prior experience of the adverse event.

Expected events are those that have been previously identified as resulting from administration of the agent. An adverse event is considered unexpected, for expedited reporting purposes only, when either the type of event or the severity of the event is not listed in:

- the current known adverse events listed in the Agent Information Section of this protocol;
- the drug package insert
- the current Investigator's Brochure

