# 5.2 Reporting Requirements

#### 5.2.1 Reporting to Principal Investigator

The Principal Investigator must be notified by study staff or co-investigators within 24 hours of learning of any serious adverse events, regardless of attribution, occurring during the study or within 30 days (refer to Section 7.1) of the last administration of the study drug.

Phone Number for Expedited Reporting:
[name]
[contact]
Alternate Phone Number for Expedited Reporting:
ALTERNATE NAME AND PHONE
[name]
[contact]

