#### 6.0 STATISTICAL ANALYSIS

# 6.1 HIFU Phase II Study

Our preliminary data suggests that up to 60% of tumors invisible to standard mpMRI are detected on hrMRI in an active surveillance population. It is unclear how many additional lesions will be identified on PSMA PET-MRI. Since all areas of concern will be biopsied and only biopsy-proven tumors will be treated with HIFU, the morbidity of the surgical intervention is minimized and its potential to achieve cure is maximized.

Power Assessment: The main hypothesis to be tested is whether the sensitivity of PSMA PET-hrMRI is greater than mpMRI alone in 20% considering the prostate divided in 6 sections for each patient. The power is evaluated using 1000 simulations based on the McNemar's type test proposed by Yang et al. (17,2010). Data is generated based on four correlations: r1: between lesions evaluated by PSMA PET-hrMRI for the same patient, r2: between lesions evaluated by mpMRI for the same patient, r3: between evaluations PSMA PET-hrMRI and mpMRI for the same lesion and r4: between evaluations PSMA PET-hrMRI and mpMRI for the different lesions at the same patient. Based on preliminary data, we estimated mpMRI sensitivity of 42%, (r1, r2, r3, r4) = (-0.249, -0.119, 0.714, -0.172) using Spearman correlation, average number of lesions of 2.5 per patient and prevalence of patients with at least one positive biopsy section equal to 82%. The results are presented in Table 1.

**Table 1.** Power for McNemar test proposed by Yang et al. (2010) to detect a difference of 20% between sensitivities of the combination (PET-hrMRI or mpMRI) and mpMRI

Total Sample # Patients with at least one positive biopsy
Size section Power

20	16	70.2
25	21	81.5
30	25	88.9
35	29	93.1
40	33	95.5

The minimum sample size to reach at least 85% of power is 30 patients with complete imaging data. Patients with incomplete imaging data will be replaced.

Statistical Analysis: Sensitivities will be compared using McNemar's type test proposed by Yang et al. (17,2010). for cluster matched binary data. In addition, the 95% confidence interval for difference between sensitivities will be calculated as proposed by Yang et al. (18,2012).

Secondary Endpoints: Negative biopsy rate within treatment zones on standard 12-core biopsy 6 months following HIFU therapy; rate of high grade cancer in the untreated lobe.

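### No adverse event review is scheduled to close the 30-day SAE window for HIFU-arm patients who receive the tracer but do not go on to HIFU

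*Combined protocol and SAP*

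**What the plan says.** **The reporting window.** Section 5.2.1 requires the principal investigator to be told within 24 hours of learning of any SAE "regardless of attribution, occurring during the study or within 30 days (refer to Section 7.1) of the last administration of the study drug". The note under the attribution categories in Section 5.1 gives the same period: "This includes all events that occur within 30 days of the last dose of protocol treatment". Section 5.1 also counts anyone who received a dose as evaluable for toxicity and part of the safety analysis.

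**What is captured.** Section 3.4.1.7: "Only grade 3 and above imaging-related AEs will be captured and all SAEs following the receipt of 18F-DCFPyL agent".

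**When someone looks.** Section 3.4.1.7: "Adverse events will be assessed at imaging, post imaging (biopsy), HIFU/Prostatectomy, and HIFU follow up". The HIFU calendar in Section 3.4.2 marks the same four points and times the last from HIFU. It requires imaging a minimum of one day before biopsy and sets no maximum.

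**Who leaves before HIFU.** Footnote 2, on the post-imaging column, reads "End of study for bilateral Gleason ≥7 disease". The section Eligibility for HIFU agrees: "If patients have high grade disease in both lobes, they will not be eligible for HIFU therapy on this trial". Footnote 1 limits on-study HIFU to patients whose high-grade disease is confirmed on one side.

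**Planning figure.** Section 6.1 assumes a "prevalence of patients with at least one positive biopsy section equal to 82" per cent; Table 1 turns this into 25 of 30 patients.

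**The concern.** The duty to report runs to day 30, but the scheduled reviews do not reach day 30 for every dosed patient. Patients who have HIFU or prostatectomy are reviewed again later, and those reviews can pick up events since the scan. HIFU-arm patients whose mapping biopsy rules HIFU out have no later column in the calendar that applies to them.

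Two kinds of event could then be missed: a late SAE after the tracer, and a serious complication of the transrectal biopsy, such as an admission after the visit. Some biopsy cores are taken only because the study scan showed a lesion, so the second kind bears on what the scan leads to. Because exit depends on the mapping result, so does the chance that an SAE is found. Any resulting error in the SAE count for the dosed population runs downward.

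**Working it through.** **1. The window against the schedule.** The 30 days are set by rule, so there is no derived figure to reproduce. Let *d* be the number of days from tracer to the post-imaging review. For a patient with no later review, the days of the window left without one are max(0, 30 − *d*).

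| *d* (days) | Days without a scheduled review | Share of 30 |
|---|---|---|
| 1 | 29 | 96.7% |
| 3 | 27 | 90.0% |
| 7 | 23 | 76.7% |
| 14 | 16 | 53.3% |
| 15 | 15 | 50.0% |
| 21 | 9 | 30.0% |
| 30 or more | 0 | 0% |

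The smallest *d* the calendar allows is 1, if the review takes place on the day of biopsy. The gap exceeds half the window only when *d* is 14 or less. The documents do not give the expected interval.

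**2. Who is affected.**
- *Bilateral Gleason ≥7.* Footnote 2 ends their study at the post-imaging stage. This is explicit.
- *Negative mapping biopsy, or Gleason 6 only.* No passage states when their study ends. Footnote 1 and Eligibility for HIFU exclude them from HIFU on study, and the two later reviews are tied to HIFU. That they have no further review is an inference.

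**3. How many.** First, the plan's own column in Table 1, as 0.82 × N:

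| N | 0.82 × N | Table 1 |
|---|---|---|
| 20 | 16.4 | 16 |
| 25 | 20.5 | 21 |
| 30 | 24.6 | 25 |
| 35 | 28.7 | 29 |
| 40 | 32.8 | 33 |

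All five entries agree after rounding. At N = 30, patients with no positive section number 30 − 25 = 5 (or 30 × 0.18 = 5.4). They cannot have confirmed unilateral high-grade disease on mapping biopsy. Bilateral and Gleason-6-only patients come on top, at rates the documents do not give.

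**4. Is the window closed elsewhere?** Section 5.2.1 points to Section 7.1 for the 30 days. Section 7.1.1 describes review of study data by the principal investigator and committee oversight, but names no window and no patient contact. No day-30 visit, call or record check appears anywhere else.

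**The case against.** The strongest reply is that SAEs are not lost. The duty in Section 5.2.1 depends neither on a calendar visit nor on the patient still being on study. Section 5.1 also covers attributed events after day 30. Patients come from the investigators' own urology practice, and the principal investigator and the monitoring committee oversee safety. This stands in part: a reader might infer that events after biopsy go unobserved, and the documents do not support that. What is absent is scheduled ascertainment. A duty triggered by learning of an event does not make anyone ask.

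Other stronger readings also fail:
- *The last review falls on biopsy day.* No passage dates it. Footnote 2 turns on pathology, so exit must await the result, and the review may be later too.
- *Most of the window is always uncovered.* This needs a review within 14 days of the tracer; at day 30 or later nothing is left uncovered.
- *Footnote 2 removes every non-HIFU patient.* It names bilateral disease only. The section HIFU Therapy and Follow Up Schedule promises the 6-month assessment to all subjects, although its heading and preceding sentence concern patients eligible for HIFU. Section 3.4.1 lets the investigator move a subject to the prostatectomy arm, which restores later reviews.
- *All biopsy complications are missed because of early exit.* Non-serious ones that are not imaging-related fall outside the capture rule in Section 3.4.1.7 for every patient. Only serious ones fall into this gap.
- *A third of the arm is affected.* Adding an assumed 10–20% of 30 (3 to 6 patients) to the 5 would give 8 to 11 of 30, but nothing in the documents supports that percentage.

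It is also fair to say that Section 3.3 lists no safety endpoint, so no primary or secondary result changes.

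**Conclusion.** The point holds as a gap in scheduled follow-up. For HIFU-arm patients who do not proceed to HIFU, the last planned adverse event review is the post-imaging one. Depending on its timing, between 0 and 29 of the 30 reportable days have no scheduled ascertainment after it. Nothing is scheduled afterwards for serious biopsy complications either.

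About 5 of 30 patients would be affected through having no positive section, if the 82% planning value holds; it is a power input rather than a forecast of HIFU ineligibility. The addition from bilateral and Gleason-6-only disease is unknown. The conclusion for patients outside footnote 2 rests on reading the HIFU-timed columns as not applying to them, and on their not switching to prostatectomy.

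The consequence is that SAE ascertainment differs by mapping result and the safety count can be biased low. The size of that bias cannot be estimated from the documents. The change is worth making because it is cheap.

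**What to change.** Add one adverse event review to the HIFU calendar at or after day 30 post-tracer, for any dosed subject proceeding to neither HIFU nor prostatectomy. Existing staff can do it by record check or telephone. Reconcile footnote 2 with the 30-day period in Sections 5.1 and 5.2.1 so that participation does not end before that review, and state when the study ends for other subjects who have no HIFU. With the review in place, the part of the window without a scheduled look falls to 0 of 30 days.

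Timing the review from the biopsy as well is optional, since the documents anchor the window to the tracer.

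Two edits can go in the same amendment: replace the pointer to Section 7.1 with the window itself, and add to Section 3.4.1.7 the 6-month review that the prostatectomy calendar already contains.

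The cost is a short contact or chart check for what is probably a minority of one arm, plus a calendar entry and a revised footnote. It needs no extra procedure or clinic visit.

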## 3.4.3 Study Intervention

## **3.4.3.1** Study Intervention(s) Administration

#### Study Interventions Description

18F-DCFPyL Injection is a radioactive diagnostic PET imaging agent indicated for (1) use in staging of men with high risk prostate cancer and (2) the detection of recurrent or metastatic prostate cancer.

## Dosing and Administration

The recommended dose of 18F-DCFPyL Injection is 9 mCi (333 MBq), administered intravenously as a bolus injection followed by a flush of normal saline. The drug product contains radioactive material and will only be handled by personnel trained and certified in the use of radioactive isotopes with proper shielding and monitoring.

## **3.4.3.2** Preparation/ Handling/ Storage/ Accountability

# Acquisition and Accountability

Progenics Pharmaceuticals will be providing the injection to the investigator.

[figure not shown]
## Formulation, Appearance, Packaging, and Labeling

18F-DCFPyL Injection is a Fluorine-18 labeled small molecule that targets the extracellular domain of PSMA. 18F-DCFPyL is a radioactive diagnostic agent used with PET imaging. Chemically, 18F-DCFPyL is 2-(3-{1-carboxy-5-[(6-[18F]fluoro-pyridine-3-carbonyl)-amino]-pentyl}ureido)-pentanedioic acid. The structural formula is:

18F-DCFPyL Injection is a sterile, clear particle-free solution for intravenous use. It is supplied at a specific activity of at least 1000 mCi/ $\mu$ mol at the Time of Administration, corresponding to a total administered chemical mass of DCFPyL of  $\leq$  4  $\mu$ g, and a radioactivity concentration of 1 to 80 mCi/mL at the Time of Calibration (TOC), or, end of synthesis (EOS). The pH is between 4.5 and 7.5. The product is to be stored at room temperature; beyond-use date is 10 hours from EOS.

Based on information provided by the cross-referenced IND 129,952, there are a total of three labels for the drug product, 18F-DCFPyL: a label on the finished drug product vial, a prescription label for the lead pig, and a label for the unit-dose syringe. The finished drug product within the vial is dispensed into unit-dose(s) at the radiopharmacy and shipped in the lead pig to the clinical site.

•The batch label of the finished drug product vial: An example label of the 18F-DCFPyL finished drug product vial from Sofie (formerly Zevacor)-Gilroy facility is provided. It complies with 21 CFR 312.6.

[figure not shown]
•The prescription label on the lead pig: This label is for the lead pig shipped from the radiopharmacy to the clinical site. The labeling provides detailed information of the drug product for the clinical sites. It is in compliance with 21 CFR 312.6 requirements.

Example prescription label on the lead pig as dispensed by the Gilroy-radiopharmacy; similar label will be prepared for Cedars-Sinai Medical Center:

•The unit-dose syringe label: This label is for the unit-dose syringe as dispensed by the radiopharmacy. The labeling provides the minimum necessary and useful information (due to the space limitation and high levels of radioactivity) of the drug product for the clinical sites during drug administration. It is in compliance with the 21 CFR 312.6 requirements.

Example label on the unit-dose syringe as dispensed by the Gilroy-radiopharmacy; similar label will be prepared for Cedars-Sinai Medical Center:

